## 7.3 Sample Size and Study Duration

A maximum of 48 subjects with locally advanced or metastatic NSCLC who undergo definitive chemoradiation will be accrued over approximately two years. The study will close when the final subject has undergone the approximately 6-month post-radiation follow-up visit.

## 7.4 Subject Population(s) for Analysis

The all-treated population will be used for all study analyses. For purposes of this study, the all-treated population is defined as the group of subjects ingesting at least 1 week of FS.

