## 2 Study Objectives

### Primary Objective:

Determine in a phase II trial whether FS supplementation decreases the risk of RILI in patients receiving definitive chemoradiotherapy for locally advanced or metastatic NSCLC, and to collect additional toxicity and tolerability data from FS administration in this population.

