### **3.2 Primary Study Endpoints**

The primary endpoints to be measured in this study include:

CONFIDENTIAL

This material is the property of the University of Pennsylvania. Do not disclose or use except as authorized in writing by the study sponsor.  
Version Date: 07/27/2017

- Rate of RILI after FS administration in a population of patients receiving definitive chemoradiotherapy for lung cancer.
- Toxicity and tolerability data of dietary FS administration during chemoradiotherapy.

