#### **4.4 Early Withdrawal of Subjects**

##### **4.4.1 When and How to Withdraw Subjects**

Any subjects experiencing a serious adverse event (SAE) felt to be related to study drug will be withdrawn from the study. Subjects will be withdrawn if discontinuation from the study is deemed by the principal investigator (PI) to be in their best interest, namely if an abnormal response of the subject's malignancy to radiotherapy outside of normal limits is observed. Subjects may be withdrawn at any time at the discretion of the PI. Any subject withdrawing their consent to participate in the study or their authorization to use their protected health information will be withdrawn from the study. Subjects withdrawn may be replaced at the discretion of the principal investigator.

Subjects may be withdrawn due to any of the following:

1. Intolerable side effects
2. Clinical deterioration
3. Failure to attend outpatient and treatment visits
4. Failure to provide lab specimens
5. Failure to cooperate and provide toxicity and tolerability measures

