##### **4.4.2 Data Collection and Follow-up for Withdrawn Subjects**

Even though subjects may be withdrawn prematurely from the study, toxicity data will continue to be assessed as part of the normal radiotherapy protocol as determined by the investigator. Routine tests will be performed as standard of care as part of the ongoing radiotherapy.

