## **5.5 Subject Compliance Monitoring**

Study subjects will be asked to complete a "FS log" during the study treatment period, and a research technician will assess treatment regimen compliance by determining quantities of FS eaten. This will occur on a weekly basis during subjects' daily visits for radiotherapy. If a subject is deemed to be significantly non-compliant with the FS diet, the reason will be documented. This will be entered in RedCap by the Clinical Research Coordinator. Patients will also get text message or phone call reminders to take their flaxseed.

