## **8.2 Stopping Rules**

If the subject develops adverse gastrointestinal complaints (Grade 3 or higher GI toxicity), or if the subject develops other significant side effects otherwise deemed unrelated to current radiotherapy, or if the subject displays unexpected lack of tumor responsiveness to radiotherapy, then the subject will be removed from the study.

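### Section 7.4 drops subjects who take less than 1 week of flaxseed from every analysis, so early intolerance and toxicity disappear from the toxicity and tolerability summaries

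*Combined protocol and SAP*

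**What the plan says.** Section 7.4 is explicit on scope: "The all-treated population will be used for all study analyses". It then sets the entry condition: "the all-treated population is defined as the group of subjects ingesting at least 1 week of FS". No separate safety population is defined anywhere.

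Toxicity and tolerability are not side issues. The primary objective in Section 2 includes the aim "to collect additional toxicity and tolerability data from FS administration in this population", and Section 3.2 lists "Toxicity and tolerability data of dietary FS administration during chemoradiotherapy" as a primary endpoint.

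Two rules take subjects off study for toxicity, and neither requires a minimum exposure. Section 4.4.1 says "Any subjects experiencing a serious adverse event (SAE) felt to be related to study drug will be withdrawn from the study". Section 8.2 removes subjects with gastrointestinal toxicity of grade 3 or worse. Section 4.4.1 also allows withdrawal for side effects the subject cannot tolerate, and replacement of withdrawn subjects at the principal investigator's discretion.

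On data after withdrawal, Section 4.4.2 says "toxicity data will continue to be assessed as part of the normal radiotherapy protocol". On adherence, Section 5.5 says "If a subject is deemed to be significantly non-compliant with the FS diet, the reason will be documented". Neither section places a subject with less than 1 week of FS in an analysis set.

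**The concern.** The population is called all-treated, but someone who takes FS for three days and stops has been treated and is not in it. For toxicity and tolerability, entry to the set therefore depends partly on the outcome being summarised: those who cannot take FS for a week are removed because they could not take it.

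The timing makes this worse. FS begins about 1 week before radiotherapy (Section 5.2), so the cut-off falls roughly where the pre-radiation week ends. That is the only time on FS when side effects are not mixed with those of radiation.

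Section 1.1 reports that the pilot's muffin formulation failed its tolerability criteria in this disease. Section 1.5 supports the new packets from cystic fibrosis and lung transplant studies. This trial is to supply the tolerability data for the packets in lung cancer patients and to inform a phase III trial. If the people who gave up first are missing from the tables, the next trial is planned on too favourable a picture.

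**Working it through.** **Design figures.** The plan states no figure for tolerability, so there is none to reproduce. Its only design calculation for a primary endpoint is the exact binomial test for RP in Section 7.2. With n = 39, rejection at 3 or fewer cases, a null response rate of 0.82 and an alternative of 0.941, I obtain a significance level of 0.0618 (stated 0.062) and power of 0.8036 (stated 80%). These figures reproduce and do not bear on this point.

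**Following one subject through the plan.**
1. The subject starts FS at Visit 1, about a week before radiotherapy.
2. On day 3 the subject stops because of taste, side effects or a reaction, or is taken off study under Section 4.4.1 or 8.2.
3. The subject has ingested less than 1 week of FS, so Section 7.4 excludes the subject from all analyses.
4. No other section brings the subject back.

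The exclusion comes from the short exposure, not from withdrawal as such. A subject withdrawn after 1 week stays in the set.

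**Size.** Let N = 48 subjects start FS (the maximum accrual in Section 7.3), T of them tolerate it, and k of the others stop for intolerance before 1 week.

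- Rate among all starters: T/48
- Rate in the Section 7.4 set: T/(48 − k)
- Bias: T/(48 − k) − T/48 = (T/48) × k/(48 − k), which is never negative

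T and k are assumptions. With T = 28:

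| k | Section 7.4 set | All starters | Bias (points) |
|---|---|---|---|
| 0 | 28/48 = 58.3% | 58.3% | 0 |
| 1 | 28/47 = 59.6% | 58.3% | 1.2 |
| 3 | 28/45 = 62.2% | 58.3% | 3.9 |
| 5 | 28/43 = 65.1% | 58.3% | 6.8 |
| 6 | 28/42 = 66.7% | 58.3% | 8.3 |

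Varying T at k = 5:
- T = 21, near the pilot FS arm's 42.9%: 21/48 = 43.8% against 21/43 = 48.8%, a bias of 5.1 points.
- T = 34, near the pilot control arm's 71.4%: 34/48 = 70.8% against 34/43 = 79.1%, a bias of 8.2 points.

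The choice k = 5 is about the 10% inevaluable allowance in Section 7.2 (0.10 × 48 = 4.8). That allowance was made for the RP sample size and is used here only to set a scale.

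Seen from the other side, suppose 5 subjects stop early for intolerance and 5 more become intolerant later. Intolerance is then 10/48 = 20.8% among all starters and 5/43 = 11.6% in the Section 7.4 set.

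**Reading of the cut-off.** Section 7.4 does not say whether 1 week means seven days on FS or a full week's quantity. The second reading would exclude more subjects.

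**The case against.** The strongest reply has five parts.

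- *The endpoint concerns the chemoradiotherapy period.* Section 3.2 is worded that way, and a subject who stops before 1 week has usually stopped by about the start of radiotherapy. But the objective in Section 2 has no such limit, and Table 1 schedules toxicity evaluation and FS log review from Week -1. This narrows the point without removing it.
- *No tolerability rate, criterion or threshold is defined for this trial.* True. The summaries are descriptive and no decision depends on a cut-off. That limits the severity, but a descriptive proportion still needs the right denominator.
- *The size is assumed.* Also true. The pilot had 7 subjects per arm, used a different formulation and gives no timing of stops. Its control arm says nothing about FS itself. It shows that early stopping is plausible and gives no rate.
- *Early serious toxicity is not expected.* Section 1.5 describes good tolerance, and Section 1.1 attributes the pilot failure to taste. But stopping because of taste is itself intolerance and is lost in the same way.
- *The data are collected and reported in any case.* Toxicity is scored at Visit 2 (Section 6.2) and assessed after withdrawal (Section 4.4.2), and events go to the IRB and DSMC (Section 8.1). This stands for collection and oversight, but none of it puts the subject into the final tables. One gap remains: the compliance checks in Section 5.5 take place at radiotherapy visits, so the reason for stopping may not be captured if a subject is withdrawn in the week before radiotherapy.

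**Conclusion.** The concern holds. Applied as written, Section 7.4 removes from the toxicity and tolerability summaries the subjects whose early stopping those summaries should show. The direction is certain: each intolerant stop before 1 week makes tolerability look better. The amount is not known. In the illustrations it runs from 0 with no early stops to 8.3 points with 6 such stops among 48 starters, and all of these figures rest on assumed values of T and k.

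The fault lies in the analysis set. It does not affect the RP design calculation or the reporting of events during the trial. The change should be made because it concerns a listed primary endpoint and costs almost nothing, but the trial's main test does not depend on it.

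**What to change.** In Section 7.4:

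1. Define a safety and tolerability population of all subjects who took any FS. Use it for every toxicity and tolerability summary, including the week before radiotherapy.
2. Count stopping before 1 week for side effects, taste or other intolerance as not tolerated.
3. Report early stops for other reasons (for example withdrawn consent, missed visits or clinical deterioration) separately by reason, with a sensitivity analysis that counts them as failures.
4. If wanted, keep the 1-week set for the biomarker analyses and as a supportive tolerability set, and state whether 1 week means days or quantity.

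This point calls for no change to the RP population, the sample size, or any withdrawal or stopping rule. The cost is a few sentences of analysis wording, plus confirmation that the reason is recorded for anyone who stops FS before radiotherapy begins. The reported tolerability rate may be less favourable as a result.

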# 8 Safety and Adverse Events

## 8.1 Adverse Event Reporting

Serious adverse events will be reported to the IRB and DSMC per institutional policy.

CONFIDENTIAL

This material is the property of the University of Pennsylvania. Do not disclose or use except as authorized in writing by the study sponsor.  
Version Date: 07/27/2017

All events meeting the DSMC reporting requirements will be entered into the mandatory Velos AE/SAE form. Once an event is entered, an e-mail alert to [name] ([[contact]](mailto:[contact])) will be sent. A study CRF will not replace the ACC central reporting form. Information in Velos will be accurately maintained and updated in a timely manner. If new/updated information is learned about the event, the event will be amended or corrected promptly. An investigator will determine the grade, attribution and expectedness of all events.

The following timeline will be adhered to for reporting events to the DSMC:

1. All grade 3 or higher events (AE or SAE) within five business days of knowledge
2. All unexpected deaths within 24 hours of knowledge.
3. All other deaths within 30 days of knowledge. Deaths of subject's off-study for greater than 30 days from the last study treatment/intervention are not reportable.

## **8.2 Stopping Rules**

If the subject develops adverse gastrointestinal complaints (Grade 3 or higher GI toxicity), or if the subject develops other significant side effects otherwise deemed unrelated to current radiotherapy, or if the subject displays unexpected lack of tumor responsiveness to radiotherapy, then the subject will be removed from the study.

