### 1.1 Background

The effectiveness of radiotherapy for thoracic malignancies is limited by the high radiosensitivity of normal lung parenchyma. Clinically significant radiation lung injury occurs in up to 30% of patients irradiated for lung cancer and 10-15% of other thoracic oncology patients. A greater proportion of patients have subclinical adverse effects of radiation on the lung, identifiable by imaging and/or physiologic testing. Highly reactive compounds known as reactive oxygen species (ROS) and reactive nitrogen species (RNS) are induced in large quantities by radiation therapy (XRT) and have been implicated in this form of lung injury.

Two phases of radiation-induced lung injury have been described in humans. Acute radiation pneumonitis, thought to be largely inflammatory and exudative in nature, can occur several weeks to six months post-irradiation, and can be life threatening if a large volume of lung has been affected. In the second phase of radiation-induced lung injury that can occur months to years after irradiation, the lung tissue enters a fibrotic state in which the numbers of inflammatory cells decrease and a marked thickening of alveolar walls occurs due to collagen deposition.

There is currently no known effective pharmacologic therapy for the prevention of acute or chronic radiation pneumonopathy. Systemic oral and intravenous corticosteroids are routinely used to treat clinically significant acute radiation pneumonitis, but the administration of these drugs does not alter the risk of developing late radiation fibrosis. The exact mechanism by which the acute radiation pneumonitis phase transitions to the late fibrotic phase is unclear. However, as recently reviewed by Robbins and Zhao, studies implicate a chronic state of oxidative stress in radiation-induced late fibrosis; it is widely recognized that irradiation is associated with both a rapid and a chronic increase in ROS/RNS production. This persistent state of oxidative stress may therefore be a target for inhibition of radiation injury and radioprotection of normal tissues to allow for more effective radiotherapy and improved clinical outcomes.

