## 7 Statistical Plan

### 7.1 Study Design

This is a single arm phase II flaxseed diet supplement for subjects with locally advanced or metastatic NSCLC who are scheduled to begin conventional chemoradiation therapy with definitive intent. Flaxseed is thought to be a protectant for radiation pneumonitis. Subjects will be told to ingest 40g of flaxseed daily.

FS will be ingested daily for 8-9 weeks, including 7-8 weeks during radiation and for 1 week prior to radiation. Subjects will be queried weekly about their FS consumption while on the diet. Serial measurements of plasma levels of flaxseed metabolites, urine levels of oxidative stress markers, and buccal swabs will be obtained at 5 time points: baseline (prior to start of radiation), at week 0 of radiation, 4 weeks into radiation, at the end of radiation and at one month post-radiation. This assessment is important because NSCLC subjects receiving radiation therapy often develop esophagitis and swallowing difficulties.

CONFIDENTIAL

This material is the property of the University of Pennsylvania. Do not disclose or use except as authorized in writing by the study sponsor.  
Version Date: 07/27/2017

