## 7.2 Statistical Analyses and Decision-making

Primary Objective: This is a single-arm phase II trial. The primary endpoint will be absence of radiation pneumonitis (RP) of grade 3 or above within 6 months from the end of RT, according to the CTCAE v.4.0 scale. The most recent pooled Radiation Therapy Oncology Group analysis showed that the rate of  $\geq$  grade 3 RP was 18%, so the null hypothesis “clinical response” rate for this study is 82%. A sample size of n=39 achieves 80% power to detect a response rate of 94.1% in a one-sided binomial exact test with target significance level no larger than  $\alpha=0.1$ . The actual significance level achieved by this test is 0.062. We will reject the null hypothesis that FS treatment has no effect on the RP rate if there are 3 or fewer cases of RP in the 39 evaluable subjects. Assuming a death rate of 10% prior to 6 months and a 10% inevaluable rate, **we will seek to enroll 48 patients**. As the Department of Radiation Oncology at Penn is one of the busiest centers in the country and currently treats approximately 235 patients daily, and the thoracic oncology service is the busiest clinic service within the Department and has exceptional rates of enrollment of patients onto investigator-initiated clinical trials, we expect to have no difficulty enrolling 48 patients in two years.

Secondary Objective: We will analyze the continuous secondary endpoints (Aim 2) using mixed linear models that include random effects for subject. We will inspect the data before analysis to identify a transformation to normality, if needed. A simpler form of the analysis would be to conduct a paired *t* test comparing baseline to post-treatment values. With n=39 evaluable subjects, we will be able to detect a change in the mean of 0.533 standard deviations with 90% power in a two-tailed test with type I error rate  $\alpha=0.05$ . We will collect blood and urine for markers of antioxidant activity and systemic inflammation, and buccal swabs for antioxidant enzyme epithelial gene expression at the specified time points. We will analyze the data using mixed linear models that include random effects for subject. This will effectively be the same as a paired *t*-test on differences across the treatment periods.

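### Subjects removed or withdrawn have no committed pneumonitis assessment over the 6-month endpoint window, and the undefined evaluable set leaves open whether they are counted

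*Combined protocol and SAP*

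**What the plan says.** **Leaving the study.** Section 8.2 lists three triggers: grade 3 or higher gastrointestinal toxicity, other significant side effects judged not to be due to the radiotherapy, and poor tumor response. The consequence is exit from the study, not just an end to FS: "or if the subject displays unexpected lack of tumor responsiveness to radiotherapy, then the subject will be removed from the study". Section 4.4.1 also lets the principal investigator (PI) withdraw a subject at any time. Its listed reasons include intolerable side effects, clinical deterioration, missed visits and missing specimens.

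**Follow-up afterwards.** Section 4.4.2 says that "toxicity data will continue to be assessed as part of the normal radiotherapy protocol as determined by the investigator". It ties routine tests to the ongoing radiotherapy. It gives no duration and mentions neither the post-radiation visits nor RP.

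**Replacement.** Section 4.4.1: "Subjects withdrawn may be replaced at the discretion of the principal investigator". No condition is set on timing or endpoint status. Section 7.3 caps accrual: "A maximum of 48 subjects with locally advanced or metastatic NSCLC".

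**Endpoint and timing.** Section 7.2: "The primary endpoint will be absence of radiation pneumonitis (RP) of grade 3 or above within 6 months from the end of RT". Section 1.1 says that acute RP "can occur several weeks to six months post-irradiation". Subjects still on study are assessed at about 1 and 6 months after radiotherapy (Sections 3.1, 6.4 and 6.5).

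**Who is counted.** Section 7.4 uses the all-treated population, meaning subjects with at least 1 week of FS, for every analysis. Section 7.2 states its decision rule for 39 evaluable subjects and allows for 10% deaths and 10% inevaluable among 48 enrolled. It does not define evaluable or say how a missing 6-month RP status is handled.

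**The concern.** The removal triggers act largely during radiotherapy, while RP can appear at any point from several weeks to six months after it. A subject who leaves during treatment therefore leaves before much of the period in which the primary event can occur, and the plan then requires no one to look for it. Some such departures are foreseeable: Section 7.1 notes that "NSCLC subjects receiving radiation therapy often develop esophagitis and swallowing difficulties", although it does not say at what grade.

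What happens to these subjects in the count is also open. Section 7.4 suggests that they stay in. The evaluable set in Section 7.2 could leave them out, and Section 4.4.1 lets the PI bring in someone else. This is an open-label single-arm trial judged on 3 versus 4 cases. Exclusion or replacement for reasons linked to the outcome could therefore decide the result. Replacing subjects who stop for intolerable side effects would also affect tolerability, which Section 3.2 lists among the primary endpoints.

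**Working it through.** **Inputs (Section 7.2).** Null RP rate 0.18 (response 0.82); alternative response 0.941 (RP 0.059); n = 39; reject the null if RP cases X ≤ 3; target one-sided error at most 0.10. The documents give no withdrawal or replacement rate, so every rate in steps 2 to 5 is an assumption.

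**1. The plan's own figures.** X ~ Binomial(39, p).
- Error: P(X ≤ 3 | 39, 0.18) = 0.00044 + 0.00373 + 0.01554 + 0.04207 = 0.0618. The stated 0.062 reproduces.
- Power: P(X ≤ 3 | 39, 0.059) = 0.804. The stated 80% reproduces.
- Expected evaluable: 48 × 0.9 × 0.9 = 38.9, about 39. The plan thus foresees about 9 of 48 subjects without a usable outcome.

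**2. k unobserved subjects counted as RP-free.** Only 39 − k can contribute a case, so the error is P(X ≤ 3 | 39 − k, 0.18).

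| k | Subjects observed | One-sided error |
|---|---|---|
| 0 | 39 | 0.062 |
| 4 | 35 | 0.103 |
| 6 | 33 | 0.131 |

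**3. A share f of RP cases withdrawn, left out of the count and replaced.** The RP rate among those counted is p = 0.18(1 − f)/(1 − 0.18f), and the error is P(X ≤ 3 | 39, p).

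| f | p | One-sided error |
|---|---|---|
| 10% | 0.162/0.982 = 0.1650 | 0.096 |
| 20% | 0.144/0.964 = 0.1494 | 0.146 |
| 30% | 0.126/0.946 = 0.1332 | 0.219 |

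**4. A single RP case replaced by a new subject at 18% risk.** The result changes only when there were exactly 4 cases and the new subject has no RP: 0.0618 + P(X = 4) × 0.82 = 0.0618 + 0.0831 × 0.82 = 0.130.

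**5. The opposite convention: lost subjects counted as failures.** With a share m lost, the response rate under the alternative is 0.941(1 − m).
- m = 5%: 0.941 × 0.95 = 0.894; power 0.40.
- m = 10%: 0.941 × 0.90 = 0.847; power 0.13.

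Handling a few subjects one way or the other can therefore take the error past its target or remove most of the power. The plan does not say which way they are handled.

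**The case against.** The case against a stronger claim is substantial, and much of it stands.

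- **Section 7.4 protects the denominator.** A subject who develops RP after radiotherapy would normally have taken 8 to 9 weeks of FS and is all-treated. On that text, a replacement adds a subject and does not delete the case. A reader might infer that the plan lets RP cases be swapped out; no written rule does so. That would need discretionary withdrawal, replacement, and a reading in which the undefined evaluable set overrides Section 7.4. What remains is that the two sections are not reconciled.
- **An observed event is not erased.** Section 8.1 requires grade 3 or higher events to reach the DSMC within five business days of knowledge. This protects events that someone learns of. It does not create an assessment for a subject no longer followed.
- **RP would not normally trigger Section 8.2.** Its side-effect clause is limited to effects judged unrelated to radiotherapy. Any route for RP runs through Section 4.4.1.
- **Section 4.4.2 states no cut-off.** A reader might infer that follow-up stops when radiotherapy does. The text says only that assessment continues, with duration and content unspecified. Loss of the endpoint is a risk, not a certainty.
- **Replacement and the cap are compatible.** Replacement is permissive and 48 is a ceiling, so they do not contradict each other.
- **Losses are budgeted.** The 10% inevaluable allowance protects sample size. It does not protect against losses related to outcome.
- **The direction of bias is not fixed.** Nothing says that unobserved subjects count as RP-free, and at 10% replacement the error is still within 0.10.

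**Conclusion.** The concern holds as an ascertainment and counting gap. Subjects leave the study rather than only FS, their later assessment is left to routine care, and no RP grading is committed over the 6-month window on which the primary decision rests. Section 7.4 largely answers who is analysed, but it cannot supply a missing outcome, and Section 7.2 does not follow its terms.

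The size depends on assumptions. The error goes from 0.062 to 0.103 with 4 unobserved subjects counted as RP-free, and to 0.096 or 0.146 with 10% or 20% of RP cases replaced and left out of the count. If 5% of subjects are lost and counted as failures, power falls from 0.80 to 0.40. These figures show how sensitive a 3-of-39 rule is; they do not predict what will happen. The documents do not support a claim that the trial is biased toward success by design. The gap should still be closed before the primary analysis, because RP status that is not collected may not be recoverable.

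**What to change.** Leave the clinical removal and withdrawal criteria as they are. Change only follow-up and analysis.

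1. In Sections 4.4.1, 4.4.2 and 8.2, state that stopping FS or being withdrawn does not end endpoint follow-up.
2. Ascertain grade 3 or higher RP through 6 months after radiotherapy, by visit or from the clinical record, for every all-treated subject unless consent is withdrawn.
3. In Section 7.2, define evaluable without reference to outcome and reconcile it with the all-treated population in Section 7.4. Prespecify how deaths and missing RP status are handled, with best- and worst-case sensitivity analyses, and give the rejection boundary for the number actually analysed.
4. Keep any replaced subject who took at least 1 week of FS in the primary analysis, within the maximum of 48.

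The cost is a wording amendment and limited chart review for a few subjects. The PI also gives up some discretion over replacement.
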